7.1 Participation Flow

Figure 1 presents the study timeline for participating families. Following initial screening and consent, families complete baseline assessment (Week 0) and eligible participants are then randomized to one of the two treatment comparators. Participants are granted up to 20 weeks to complete their allocated treatment program. The decision to allow a 20-week treatment window was informed by PFAC and stakeholder input urging that an appropriate and realistic timeframe for treatment would be one that allows for periodic missed sessions, holiday breaks, health-related cancellations, and attendance-interfering life events. All randomized families are invited to complete a midtreatment assessment once they complete half of their allocated treatment. Families who do not complete half of their allocated treatment by the end of the second month of their treatment phase are invited to complete a midtreatment assessment at Week 8. All randomized families are invited to complete a posttreatment assessment once they fully complete their allocated treatment program. Families who do not complete their allocated treatment program by the end of the fifth month of their treatment phase are invited to complete a posttreatment assessment at Week 20. All randomized families are invited to complete a follow-up assessment at Week 52.

Figure 1.

Note: Week numbers reflect target number of weeks since baseline that participants in the Kids FACE FEARS Trial will complete assessments at each timepoint.

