Although a number of established and highly overlapping Therapist-Led CBTs for youth anxiety exist, the well-supported *Cool Kids* CBT suite for youth anxiety^{99,100} was selected for several important reasons. First, *Cool Kids* includes all the “gold standard” CBT components for treating youth anxiety and has an extensive research base.^{101–103} Second, *Cool Kids* is a time-limited and relatively brief suite of treatment programs delivered across roughly 3 months, which accommodated the PFAC and stakeholder advisor suggestion for relatively short-term treatment. Third, the *Cool Kids* suite of treatment programs comprehensively includes developmentally tailored versions for the full age range of youth included in the study (7–18 years). Fourth, the *Cool Kids* treatment suite has a documented history of successful implementation when rolled out on large-scale levels.^{103,104} Fifth, a parallel self-administered online version of *Cool Kids* teaches youth the same anxiety management skills as the therapist-led version, and in a roughly comparable number of sessions/modules, thus allowing for well-matched and time-equitable comparisons. And finally, the *Cool Kids* therapist-led and online treatment programs are all available in English and in Spanish.

The standard *Therapist-Led Cool Kids Therapy for Anxiety (ages 7-12)*⁹⁹ is a structured, evidence-based, 10-session program for treating youth anxiety in middle childhood and entails ten 50-minute weekly sessions with children and families. Therapists teach youth and caregivers core CBT components including anxiety psychoeducation, cognitive/coping skills for thinking more realistically and adaptively, problem-solving skills, and graded exposures to anxiety provoking situations. Caregivers and youth are taught skills for managing anxiety and for reducing avoidant behaviors. Caregivers are included in all sessions (adjusted developmentally) and are taught parenting skills plus personal anxiety management. The program is supported by

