To expand the accessibility and reach of CBT for anxious youth, a suite of self-paced, online, multimedia, CBT-based programs for youth anxiety was developed to run parallel to the therapist-led *Cool Kids* program. This online suite of programs covers identical content in a largely self-administered format. Similar to Therapist-Led *Cool Kids*, the *Cool Kids Online* suite of programs is comprised of separate developmentally tailored online programs, two of which were used in the present trial, depending on the age of the child: (1) “Cool Kids Online” for ages 7-12 years, and (2) “Chilled Out” for youth ages 13-18.^{54,105,106} These programs consist of 8 modules that are to be completed on a roughly weekly basis allowing for well-matched and time-equitable comparisons to the Therapist-Led CBT comparator. The online programs have already been used in numerous countries and are available in multiple languages, including Spanish. The programs include the same core CBT components as the Therapist-Led *Cool Kids* programs, feature interactive, engaging formats, and include video and audio clip examples of how to implement skills. In Cool Kids Online, caregivers take on the role of their child’s coach, helping them put their skills into practice, and learn helpful ways of responding to their child’s anxiety. In the Chilled Out adolescent online version, the teen takes primary responsibility for program completion, and there are features designed to specifically increase teen engagement—e.g., there are real teens featured in the videos, teens demonstrate skills for managing anxiety, and there is a “playlist” menu where teens can choose to re-visit content and cover skills at their own pace. The programs were originally developed in Australia. For both Cool Kids Online and Chilled Out, “Americanized” versions of the programs were used that include videos with diverse representation (e.g., American children, families, and experts; broader representation of individuals of color; removed Australian accents or vernacular).

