7.15.4 Retention and Study Compensation

Based on similar studies conducted in usual care settings that do not provide free study treatment, we expect roughly 30-50% attrition by the final follow-up timepoint, and roughly 10% of data points to be missing with each collected timepoint. REDCap surveys will be configured to minimize missing values (e.g., requiring participants to complete each item, or explicitly indicate “refuse to answer” before proceeding to the next item; providing real time alerts to the data management team when items or entire forms are missing). Data will additionally be checked on a weekly basis by a research supervisor, and patterns of missingness will be identified and corrected in real time throughout the study. To further reduce instances of missing data, we have kept the number of study forms to a minimum in order to minimize the burden to participants, and participants will be provided compensation for their time completing study forms. Finally, participants will be compensated for the burdens of completing study assessments (see below).

Given the aim to evaluate treatment engagement and performance under typical circumstances, families are not compensated for participating in treatment. To ensure generalizability and observe the treatment comparators under natural conditions, treatment is not funded by the study nor offered for free. Rather, treatment is to be paid for via the natural channels of payment in the participating health centers (e.g., insurance and co-payments). In contrast, families are compensated for participation in study assessments that are not part of the treatment comparators under study. Specifically, families will receive the following compensations for completing various study assessment components:

- a. \$50 for baseline assessment (staggered payments: \$25 following baseline questionnaires and \$25 following baseline PARS completion)
- b. \$25 for midtreatment assessment
- c. \$50 for posttreatment assessment
 - i. \$30 additional compensation for completing posttreatment PARS assessment
- d. \$100 for completing follow-up assessment

*Coaches (who are not guardians) will not receive compensation for the assessments they complete. Compensation will only be provided to the youth and guardian informants. One ClinCard that will be loaded with the above payments will be given to each family for each child enrolled in the study.

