examining heterogeneity of treatment effects (Aim II). These analyses were conducted with G*power using the repeated measures analysis of variance (ANOVA) test. Repeated measures ANOVA is similar to a mixed model in some respects, but simpler and uniformly less powerful⁸⁰ using the repeated measures ANOVA, therefore, offers a conservative estimate of the effects able to be detected with each mixed model. With $N = 300$, $\alpha = .05$, power = .8, two treatment conditions, four measurements, and a correlation between repeated measures of .5, the trial was powered to detect moderation effects as small as Cohen's $d = 0.068$. This is 7% of a SD difference and a very small effect.

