For primary analyses on the dichotomous categorical outcomes PARS Treatment Responder Status at posttreatment, baseline PARS scores will be examined for each participant to determine their individual thresholds for classification as Treatment Responders (i.e., 35% PARS score reduction). These thresholds will be used to classify each participant's statuses as posttreatment. Logistic regression models will examine Treatment Condition (along with the study covariates) as a predictor of Treatment Responder Status and Remission Status at post. For primary analyses on continuous outcomes of Treatment Satisfaction at post, linear regression models will examine Treatment Condition (with the study covariates) as a predictor of caregiver- and youth-reported posttreatment satisfaction.

7.16.5 Heterogeneity of treatment effects. For Aim II analyses (heterogeneity of treatment effects) predictor and moderator terms will be added to the models predicting youth anxiety severity that were outlined above. For study covariates being considered as predictors/moderators (e.g., language of care, youth age, youth gender, youth race, youth ethnicity, and family resource security), this will entail only adding interaction terms, as the main effects of these variables will already be in the models. For the additional variables considered as treatment moderators that are not already included as model covariates (e.g., caregiver nativity) this will entail adding main effects and interaction terms to the models. For each model examining heterogeneity of treatment effects, the relevant terms of interest will be the 2-way interaction of Variable \times Time (reflecting whether the variable uniformly predicted change across the two treatments) and the 3-way interaction of Variable \times Treatment Condition \times Time (reflecting whether the variable moderated treatment effects; i.e., whether the variable predicted differential response across the treatments). As with the Aim I comparative effectiveness analyses, log transformations of Time will be entered to consider non-linear models of change. Significant interactions will be followed up with post-hoc probing on subgroups to clarify the nature and direction of interaction, and results will be plotted for visual depiction.

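### Section 7.16.1: the Aim II sensitivity figure of 0.068 is a Cohen's f, not a d; it is not 7% of an SD, and the listed inputs name no moderator

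*Combined protocol and SAP*

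**What the plan says.** Section 7.16.1 of the combined protocol and SAP bases N = 300 on the Aim I comparison. It then reports a sensitivity analysis for the Aim II moderation analyses, run in G*Power with the repeated-measures ANOVA test. The inputs are N = 300, alpha .05, power .8, "two treatment conditions, four measurements, and a correlation between repeated measures of .5". The result is that "the trial was powered to detect moderation effects as small as Cohen's $d = 0.068", followed by: "This is 7% of a SD difference and a very small effect". The section adds that ANOVA is less powerful than the mixed model, so the figure is conservative.

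Section 7.16.5 defines the moderation test as the three-way Variable × Treatment Condition × Time term, which shows "whether the variable moderated treatment effects; i.e., whether the variable predicted differential response across the treatments". Time is to be log-transformed.

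On retention, section 7.15.4 says "we expect roughly 30-50% attrition by the final follow-up timepoint, and roughly 10% of data points to be missing with each collected timepoint". Attrition is not among the listed inputs of the sensitivity analysis.

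**The concern.** A three-way interaction in 300 participants cannot plausibly be detected with 80% power at 0.07 SD. G*Power's repeated-measures ANOVA works in Cohen's f, so a mislabelled f is the obvious candidate. The inputs also describe two conditions by four measurements, with no third factor.

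This is the only sensitivity figure given for Aim II, which is meant to inform treatment personalization. A reader who believes 0.07 SD is detectable would take a null moderator result as strong evidence that subgroups respond alike. In fact the trial could easily miss a moderate difference.

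**Working it through.** **1. Reproduce the stated figure.** Inputs from section 7.16.1: N = 300, m = 4 measurements, ρ = .5, k = 2 groups, alpha .05. Sphericity is assumed. For a within or within-between test:

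- λ = f²·N·m/(1 − ρ) = f² × 300 × 4/0.5 = 2400 f²
- df1 = 3, df2 = (300 − 2) × 3 = 894
- Power .80 needs λ = 10.95, so f = √(10.95/2400) = 0.0675.
- At f = 0.068, λ = 11.10 and power is 80.6%.
- If 0.068 is a two-group d, then f = 0.034, λ = 2.77 and power is about 25%.

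The number reproduces on the f scale only. Other G*Power designs with the same inputs:

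| Design | f at 80% power |
|---|---|
| Two groups, within or within-between, 3 df | 0.0675 |
| Balanced four cells, 3-df interaction (df 3, 888) | 0.0675 |
| Four groups, 9-df interaction | 0.081 |
| Between-factor, λ = f²Nm/(1 + (m − 1)ρ) | 0.128 |

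**2. Convert f = 0.0675 to SD units.** Let D be the largest difference and p the pattern over the four visits, with population SD s(p). For Treatment × Time, f = D·s(p)/2, so D = 2f/s(p). For a balanced 2 × 2 three-way term, D = 4f/s(p).

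| Pattern | s(p) | Two-arm D | Three-way D |
|---|---|---|---|
| (0, 0, D, D) | 0.500 | 0.27 | 0.54 |
| (0, D, D, D) | 0.433 | 0.31 | 0.62 |
| (0, D/2, D, D) | 0.415 | 0.33 | 0.65 |
| Linear over visits | 0.373 | 0.36 | 0.73 |
| log(week + 1), weeks 0/8/20/52, scaled to Week 20 | 0.483 | 0.28 | 0.56 |
| Same, scaled to Week 52 | 0.370 | 0.36 | 0.73 |

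**3. The planned three-way term as a one-df log-time effect.** Assumptions not in the documents: complete data, SD 1 at each visit, compound symmetry with ρ = .5, and time t = log(week + 1).

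The assessment weeks are also assumed. Section 7.1 says "All randomized families are invited to complete a posttreatment assessment once they fully complete their allocated treatment program", with Weeks 8 and 20 as fallback dates for midtreatment and posttreatment. Section 7.2 describes a therapist-led program that "entails ten 50-minute weekly sessions with children and families", and says of the online programs: "These programs consist of 8 modules that are to be completed on a roughly weekly basis". This supports posttreatment at about Week 8 or 10 for families who keep pace; Week 12 is a further illustration. These sections contain no error on this point.

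The per-person SD of the slope, scaled to time t*, is s = t*·√(0.5/Σ(t − t̄)²). The detectable effect is 2.80 × SE, where:

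- balanced binary moderator: SE = s·√(16/300)
- 25/75 binary moderator: SE = s·√((4/300)(1/.25 + 1/.75))
- continuous moderator, per SD: SE = s·√(4/300)

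Example for weeks 0/4/8/52 at post: Σ(t − t̄)² = 8.06 and t* = log 9 = 2.197, so s = 0.547. Then 2.80 × 0.547 × 0.2309 = 0.354 SD.

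| Case | Binary 50/50 | Binary 25/75 | Continuous, per SD |
|---|---|---|---|
| 0/4/8/52, post | 0.354 | 0.409 | 0.18 |
| 0/5/10/52, post | 0.386 | 0.446 | 0.19 |
| 0/6/12/52, post | 0.411 | 0.475 | 0.21 |
| 0/8/20/52, post | 0.474 | 0.547 | 0.24 |
| Same schedules, Week 52 | 0.618–0.640 | 0.71–0.74 | 0.31–0.32 |
| Baseline-to-post change score (s = √(2(1 − .5)) = 1) | 0.647 | 0.747 | 0.32 |

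**4. Size of the overstatement, complete data.**

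- Balanced binary: 0.354/0.068 = 5.2 to 0.730/0.068 = 10.7. Power at a true 0.068 SD is 6–8%.
- Continuous: about 2.6 to 4.8 times. Power at 0.068 SD per moderator SD is 9–19%.
- A true 0.3 SD effect with a balanced binary moderator has about 66% power in the most favourable case and about 25% on the change score.

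**5. Dropout.** Section 7.15.4 gives the endpoint, not the path. Assume retention at mid, post and Week 52 of 90/80/70% or 80/65/50%. The balanced binary effect at post then becomes 0.401 or 0.451 (weeks 0/4/8/52) and 0.523 or 0.574 (weeks 0/8/20/52). These use observed data; section 7.16.2.2 plans multiple imputation.

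**The case against.** **The SD magnitudes depend on the reviewer's assumptions.** This stands. Moderator split, time coding, assessment weeks and retention path are not fixed in the documents, so the figures in steps 3 to 5 are illustrations. The relabelling from d to f needs none of them.

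**Many planned moderators are scores, not binary groups.** This also stands. Age, attitudes and multi-item scales are candidates. A reader might infer that the 5- to 11-fold overstatement applies to all of Aim II; it applies only to balanced binary moderators, and the continuous range is smaller.

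**The missing moderator does not prove that the wrong test was run.** Correct. A reader might infer that G*Power was run on the Aim I Treatment × Time test. A balanced four-cell 3-df test also gives 0.0675, so the value cannot show which design was used. It can only be said that the listed inputs name no moderator. Under either design, 0.0675 is an f and far exceeds 0.07 SD.

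**ANOVA is conservative, so the mixed model will do better.** The one-df log-time model in step 3 does better at post in the illustrated cases, yet still needs at least 0.35 SD (balanced binary) or 0.18 SD (continuous). Its advantage was examined only where the true trajectory follows log time, so the general claim is neither shown nor refuted here.

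**Aim II is secondary, and no decision rule uses 0.068.** True, and it limits the severity. The remaining harm is over-reading null moderator results.

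**Conclusion.** The figure is wrong as written. Given section 7.16.1's own inputs and sphericity, 0.068 is Cohen's f. The d label, the 7% reading and the description as very small do not follow. This part is firm.

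The detectable three-way effect is several times larger than stated: about 0.35–0.73 SD for a balanced binary moderator and 0.18–0.32 SD per moderator SD for a continuous one. These ranges rest on complete data, compound symmetry with ρ = .5 and the stated time patterns. Uneven splits and the expected attrition make them larger.

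Two stronger readings are not supported. One is that the trial can never detect an effect near 0.07 SD; the correct statement is that it cannot do so with 80% power. The other is that the sample size is undermined; section 7.16.1 rests N = 300 on Aim I, so only the Aim II sensitivity statement is affected. It should be fixed.

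**What to change.** In section 7.16.1:

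- Delete the d label on 0.068 and the sentence that follows it (7% of an SD, very small effect). If the value is kept, relabel it Cohen's f and name the G*Power test and the effect it refers to.
- Have the trial statisticians recompute the detectable Variable × Treatment Condition × Time effect. State it with its assumptions: binary split or per SD of a continuous moderator, contrast, assessment weeks, time coding and retention.
- Recheck the statement that ANOVA is conservative against that calculation before keeping it.

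The cost is one short recalculation and a text edit. Sample size, design and the Aim I analyses do not change. The downside is a less favourable stated sensitivity for Aim II.

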7.16.2 Handling of Missing Data

7.16.2.1 Prevention and monitoring. All study data will be collected via electronic capture and communication directly with the study team. Based on similar studies conducted by our group and in related research in similar settings, we expect roughly 10% of data points to be missing. REDCap surveys will be configured to minimize missing values (e.g., requiring participants to complete each item, or explicitly indicate "refuse to answer" before proceeding to the next item; providing real time alerts to the data management team when items or entire forms are missing). Data will additionally be checked on a weekly basis by a research supervisor, and patterns of missingness will be identified and corrected in real time throughout the study. To further reduce instances of missing data, we have kept the number of study forms to a minimum in order to minimize the burden to participants, and participants will be provided compensation for their time completing study forms. Finally, participants will be compensated for the burdens of completing study assessments at a rate of \$50 for baseline assessments (including PARS) and, \$25 for midtreatment assessments, \$50 for posttreatment assessments (including PARS), \$100 for week 52 assessments and \$30 for completion of PARS at posttreatment (note: compensation will not be provided for completion of measures that will be included as part of routine care). Coaches will not receive compensation for the assessments they complete.

7.16.2.2 Statistical handling of missing data. All analyses will consist of intention-to-treat models drawing on all available data. To account for missing data, we will employ multiple imputation. Recommended procedures for single and multilevel multiple imputation will be conducted using BLIMP software, using fully conditional specification multiple imputation (FCS-MI). For each model, 50 datasets with imputed values will be created using other model covariates as predictors of missingness. Model convergence will be assessed across 8 Markov Chain Monte Carlo (MCM) processes and verified for potential scale reduction (PSR) factor<1.05. Main analyses will be conducted on the imputed dataset and the results will be pulled for final estimates (using R 4.4.1 mitml for imputation pooling per Rubin's rules, and lme4 for multilevel models, or lm and glm for linear and logistic regression models).

7.16.2.3 Reporting dropout and missing data. All instances of study dropout will be documented, including the reason for dropout, who decided that the participant would drop out (i.e., parent or guardian, therapist, study staff, adolescent patient), and whether the dropout resulted from burden of intervention, study assessment, or both. Withdrawn participants will be encouraged to continue to participate in study assessments throughout the follow-up period in order to optimize intention-to-treat models. A CONSORT diagram will account for all participants across the study.

7.16.2.4 Loss to Follow-up and Withdrawal from Treatment. This study will be using an intent-to-treat analysis so once a participant is randomized, they will always be included in analysis. If participants do not complete their entire treatment program (or withdraw from treatment) or take longer than 20 weeks, all post and follow-up assessments will still be sent to them at the indicated time points and local RAs will still perform follow-up procedures to assist with data collection.

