6.3 Study Population

6.3.1 Number of Participants. Power analysis (accounting for an expected attrition and missing data) indicated we require 150 participants per group, for a total of 300 participants in the study.

6.3.2 Eligibility Criteria. The study eligibility and inclusion, and exclusion criteria for families include:

Inclusion/ Eligibility

- Elevated child/adolescent anxiety - Operationalized as T-Score on the PROMIS Pediatric Short Form-Anxiety Scale v2.0 ≥ 55 (Child eligible if *either* the Pediatric Self-Report *or* the Parent Proxy Report score was ≥ 55)
- Child aged 7-18 years (inclusive) at time of screening
- Child and caregiver(s) are fluent in English or Spanish
- If taking medication for emotional problems, child must be on a stable dose (Operationalized as no adjustments to prescription for ≥ 8 weeks)

Exclusion Criteria

- Severity requiring higher level of care, as defined by any of the following:
 - Suicidal thoughts or behaviors (STB) with *active* plan or STB(s) that required a higher level of care within the past 6 months (e.g., inpatient, partial hospitalization)
 - Anxiety-related absences $\geq 50\%$ of school days over the past month (If summer, attendance during last month of previous school year considered)
 - Substance use that required emergency services or inpatient/partial hospitalization within past 3 months

- Clinician determined child requires higher level of care than outpatient services
- History of diagnosed autism spectrum disorder or intellectual disability with severe challenges and needs for support (e.g., complete absence of verbal communication unrelated to anxiety)
- Currently engaged in CBT or planning to continue different therapy for anxiety during study treatment phase
- Child is a ward of the state

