7.16 Statistical Considerations

Study results will be reported according to CONSORT guidelines.

7.16.1 Sample size determination. Power analysis to determine the appropriate sample size for the trial had to take into account data clustering and repeated measurements. Study data were clustered in multiple ways, resulting in non-independent observations and inflated type I error. First, there were multiple observations per child due to the repeated measures design with four major assessment points. Second, there was additional clustering due to multiple children from each site. The intraclass correlation (ICC) is a quantitative estimate of clustering and allows for adjustment for non-independence. Study investigators estimated an ICC of .5, meaning it was anticipated that 50% of the variation in the observations would be due to differences between individuals and between sites (the remaining 50% of the variation was assumed to be due to individuals varying in their responses over time). The design effect (DE) reflects the extent to which standard errors are deflated if clustering is ignored. The DE is equal to $1 + (m - 1) \times \text{ICC}$, where m is the number of repeated measures. Accordingly, with 4 time points and an assumed ICC of .5, the design effect was calculated to be 2.5. Any sample size estimate must be multiplied by 2.5 in order to obtain a sample size appropriate for the observed clustering while maintaining nominal alpha and power levels.

The required study sample size was calculated via conventional methods for repeated measures / mixed models analysis. Required sample size is a function of the alpha (type I error rate) and beta (1 – power) values. Required size per group is: $n = 2 * (Z_{1-\alpha} + Z_{1-\beta})^2$. Before adjusting for the DE, these computations found $n=60$ was required in each group for an $\alpha=.05$ (assuming family-wise error rates=.05 across the study to account for multiple comparisons) and $\text{power}=.8$ (corresponding to $\beta=.2$). After adjusting for the DE of 2.5, this power analysis indicated $n=150$ was required per group (60×2.5), for a total of $N = 300$.

The needed sample size of $N = 300$ (outlined above) was based on the primary comparative effectiveness tests of this study (Aim I). That said, a sensitivity analysis was also conducted to evaluate the magnitude of effects that could be detected in moderation analyses

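### The statistical section carries forward only a 10% missing-data figure, omits the 30-50% attrition expected in 7.15.4, and leaves the stated power and Week 52 precision unsupported at that attrition

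*Combined protocol and SAP*

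**What the plan says.** Three places in the combined protocol and SAP bear on expected data loss.

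- **7.15.4 (Retention and Study Compensation)** gives two rates in one sentence: "we expect roughly 30-50% attrition by the final follow-up timepoint, and roughly 10% of data points to be missing with each collected timepoint".
- **7.16.2.1 (Prevention and monitoring)** gives one: "we expect roughly 10% of data points to be missing". Much of the surrounding text repeats 7.15.4, but the attrition figure and the per-timepoint qualifier are absent. Neither section refers to the other.
- **6.3.1 (Number of Participants)** states: "Power analysis (accounting for an expected attrition and missing data) indicated we require 150 participants per group". It names no rate.

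Section 7.16.1 sets out the sample size. It starts from 60 per group at alpha .05 and 80% power. It then applies a design effect, "with 4 time points and an assumed ICC of .5, the design effect was calculated to be 2.5", and arrives at 150 per group. No step for attrition or missing data is shown, and no effect size is given for the primary tests.

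**The concern.** Someone who reads only the statistical section would take 10% as the whole expected loss. Someone who reads the retention section would expect between three and five in ten families to be gone by Week 52. The two readings diverge most at Week 52, where Aim I makes its longer-term comparison and 7.16.4 promises Cohen's d on model means.

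Section 6.3.1 adds to the difficulty. It assures the reader that attrition was allowed for, but the reader cannot tell which rate was used, and the calculation in 7.16.1 shows neither. What is at stake is whether 80% power, and the precision at one year, can be relied on under the attrition that the plan itself expects.

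**Working it through.** **1. The plan's own figures.** Design effect: 1 + (4 - 1) x 0.5 = 2.5. Then 60 x 2.5 = 150. Both reproduce. The 60 does not follow from stated inputs: the formula as printed, 2(Z + Z)^2, gives 15.7 two-sided or 12.4 one-sided. Reaching 60 needs a standardised difference of sqrt(15.7/60) = 0.511 two-sided (0.454 one-sided), which the documents do not state. An explicit allowance applied to 150 would have shown as 150/0.90 = 167, 150/0.70 = 215 or 150/0.50 = 300 per group.

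**2. Families left at Week 52.** 150 x 0.70 = 105 and 150 x 0.50 = 75 per arm. If a further 10% of those still in the study miss the visit, 94.5 and 67.5.

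**3. Can 10% be the total?** Take four visits and a complete baseline, since 7.15.4 says families without a baseline assessment are not randomized. Apply 10% intermittent loss to retained families at each later visit.

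| Attrition pattern | Share of data present at the four visits | Missing, all points | Missing, post-baseline points |
|---|---|---|---|
| 30%, all at Week 52 | 1, .90, .90, .63 | 14% | 19% |
| 50%, all at Week 52 | 1, .90, .90, .45 | 19% | 25% |
| 30%, even | 1, .81, .72, .63 | 21% | 28% |
| 50%, even | 1, .75, .60, .45 | 30% | 40% |

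Without intermittent loss, the all-points figures are 7.5% and 12.5% (all at Week 52) and 15% and 25% (even).

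**4. What this could mean for power.** The documents give no dropout pattern, effect size or sidedness, so this step is illustrative. Assumptions: visits at Weeks 0, 8, 20 and 52; compound symmetry with correlation .5 (the plan's value); complete baseline; two-sided .05; time as log(week + 1) for the slope; and 80% power when 10% is missing independently at each post-baseline visit. From the generalized-least-squares information, r is the ratio of standard errors to that reference, and

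power = Phi[(1.960 + 0.842)/r - 1.960].

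Example: Week 52 contrast, even dropout to 50%, r = 1.246, so Phi(2.802/1.246 - 1.960) = Phi(0.289) = 61%.

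| Quantity | Dropout | 30% attrition: r, power | 50% attrition: r, power | Power with 10% intermittent loss added (30% / 50%) |
|---|---|---|---|---|
| Treatment x log-time slope | all at Week 52 | 1.04, 77% | 1.09, 73% | 75% / 70% |
| | even | 1.08, 74% | 1.17, 67% | 72% / 64% |
| Baseline-to-Week-52 contrast | all at Week 52 | 1.09, 73% | 1.23, 62% | 70% / 59% |
| | even | 1.10, 72% | 1.25, 61% | 69% / 58% |

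If 80% is instead anchored at complete data, even dropout without intermittent loss gives 72% and 64% for the slope, and about 70% and 58% for the Week 52 contrast. Attrition that falls only at Week 52 costs the posttreatment contrast nothing.

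**5. A simpler scale.** The difference detectable at one visit with 80% power, two-sided .05, using observed cases only, is 2.802 x sqrt(2/n): 0.34 SD at 135 per arm (10% loss at that visit), 0.39 at 105 and 0.46 at 75.

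**The case against.** The best defence is that nothing here is contradictory. Section 7.15.4 states both rates together, as different quantities: families lost by the end, and data points missing. Section 7.16.2.1 merely repeats the second. This stands. A reader might infer that the two figures are incompatible, and the documents do not support that.

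It can also be said that 30-50% attrition falling wholly at Week 52 averages 7.5-12.5% of all points, which is roughly 10%. The arithmetic is right, but it leaves out the separate loss that 7.15.4 expects, "roughly 10% of data points to be missing with each collected timepoint". With that included, the total is 14-19%. An average of 10% would also hide 30-50% loss at the visit that matters most.

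A reader might take 7.15.4 to contradict itself, because 10% lost at each of three visits compounds to 1 - 0.9^3 = 27%, short of 30-50%. That holds only if the 10% is meant as the source of the attrition, which the sentence does not say.

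On power, the defence is strong. Neither rate is an input to 7.16.1, so a mismatch between two sentences costs no power in the documented calculation. Real attrition would, whichever sentence is right. Anchoring 80% at 10% loss is an assumption made here, since 7.16.1 states 80% with no missing-data term. Because the 60 cannot be rebuilt, an allowance hidden inside it cannot be strictly excluded, although the text derives it from alpha and power alone. The single-visit differences in step 5 also ignore the partial data that the planned mixed models and imputation would use.

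**Conclusion.** The point holds as an unreconciled planning assumption. Section 7.16.2.1 understates the loss that 7.15.4 expects: with both stated losses and complete baseline data, the total is about 14-30% of all data points depending on when families leave, not 10%. Attrition alone leaves 75-105 per arm at Week 52. Section 6.3.1 claims an allowance that 7.16.1 does not show, so 80% power and the Week 52 precision are unsupported at the expected attrition.

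A reader might go further and infer a definite power cost, or an error in the sample-size multiplication. Neither follows. The step from 60 to 150 is correct arithmetic and uses neither rate. Any power figure depends on the dropout pattern, the contrast, the sidedness and the reference point for 80%, none of which the documents settle for this purpose. Under the assumptions in step 4, power ranges from 77% (log-time slope, 30% late attrition) to 58% (Week 52 contrast, 50% even attrition plus intermittent loss). That is a conditional range, not a finding about the plan's own calculation.

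**What to change.** 1. In 7.16.2.1, restate the 7.15.4 expectation: 30-50% attrition by Week 52, or about 75-105 per arm before intermittent loss.
2. Define the 10%. If it means intermittent loss among families still in the study, say so, and do not present it as the total.
3. Give the power or detectable difference for the planned mixed model at posttreatment and at Week 52 under those rates, with the assumed effect size, sidedness and correlation. Show by-visit dropout and any power loss as ranges over stated assumptions, because 7.15.4 gives no visit-by-visit attrition.
4. In 6.3.1, either identify the allowance for attrition and missing data within the 150, or remove the statement that one was made.

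The cost is a wording change in the protocol and SAP plus one recalculation. No additional patients or assessments are needed. The stated Week 52 precision will probably look less favourable.
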